1.3. Statistical Hypotheses for Trial Objectives

The hypothesis for this study is that, at least one dose of intranasal esketamine (28, 56, and 84 mg) is superior to intranasal placebo in improving depressive symptoms in Japanese subjects with TRD, as assessed by the change from baseline in the MADRS total score at the end of the double-blind induction phase.

1.4. Sample Size Justification

The sample size for this study was calculated assuming a treatment difference for the double-blind induction phase of 4, 4.5, 5 points in MADRS total score between each dose (28 mg, 56 mg, 84 mg) of esketamine and the placebo respectively, a SD of 10 for each treatment group, a 1-

sided significance level of 0.05 and a drop-out rate of 12.5%. A total of 183 subjects will need to be randomized to treatment in a 2:1:1:1 ratio (72 subjects on placebo group and 37 subjects per intranasal esketamine dose group) to achieve 80% power to detect difference for at least one dose group of intranasal esketamine to placebo using a Dunnett adjustment. The treatment difference and SD used in this calculation were assumed based on results of Panel B of the ESKETINTRD2003 study with clinical consideration.

1.5. Randomization and Blinding

Randomization will be with an allocation ratio of 2:1:1:1 to intranasal placebo, intranasal esketamine 28 mg, intranasal esketamine 56 mg, or intranasal esketamine 84 mg. Randomization will be used in the double-blind induction phase to avoid bias in the assignment of subjects to treatment, to increase the likelihood that known and unknown subject attributes (eg, demographics and baseline characteristics) are evenly balanced across treatment groups, and to enhance the validity of statistical comparisons across treatment groups. Blinded treatment will be used to reduce potential bias during data collection and evaluation of clinical endpoints in this phase. Measures will be taken to ensure that the study subjects and study staff are not unblinded.

The placebo group is included in this design to maintain blinding in the double-blind phase of the study. A placebo group is necessary to allow an accurate assessment of the safety and efficacy of the study drug.

Randomization will be employed only in the double-blind induction phase of the study. Central randomization will be implemented in this study. Subjects will be randomly assigned to 1 of 4 treatment groups in a 2:1:1:1 ratio based on a computer-generated randomization schedule prepared before the study by or under the supervision of the sponsor. Randomization will be balanced by using randomly permuted blocks across the 4 treatment groups. The interactive web response system (IWRS) will assign a unique treatment code, which will dictate the treatment assignment and matching study drug kit for the subject.

The investigator will not be provided with randomization codes. The codes will be maintained within the IWRS, which has the functionality to allow the investigator to break the blind for an individual subject.

Data that may potentially unblind the treatment assignment (eg, intranasal study drug plasma concentrations, treatment allocation) will be handled with special care to ensure that the integrity of the blind is maintained and the potential for bias is minimized. This can include making special provisions, such as segregating the data in question from view by the investigators, clinical team, or others as appropriate until the time of database lock and unblinding.

At the end of the double-blind induction phase the database will be locked for the analysis and reporting of this phase. The subject treatment assignment will be revealed only to sponsor's study staff. The investigators and the site personnel will be blinded to the treatment assignment until all subjects have completed study participation through the follow-up phase.

2. GENERAL ANALYSIS DEFINITIONS

2.1. Analysis Phases

There are 5 analysis phases defined in this study:

- *A Double-blind Induction Phase*
- *A Double-blind Follow-up Phase* (Non-Responders or subjects who withdraw from DB induction phase)
- *A Posttreatment Phase* (Responders only)
- *An Open-Label Induction Phase* (Responders only)
- *An Open-Label Follow-up Phase* (Responders only)

Each analysis phase has its own analysis phase start and end dates.

2.1.1. Study Reference Start and End Dates

The reference start date for the study is defined as the date of the first dose of intranasal study medication (the date is missing for screened subjects who did not take any intranasal study medication). The reference end date for the study is the end of trial date including the last follow-up visit.

2.1.2. Analysis Phase Start and End Dates

Double-blind Induction Phase

The start date of the double-blind induction phase (referred to as ‘DB start date’) is the date of the first dose of intranasal study medication. The double-blind induction phase end date (referred to as ‘DB end date’) is the maximum of the date of the last visit in the double-blind induction phase and the date of completion/withdrawal from the double-blind induction phase.

The start date/time of the double-blind induction phase (referred to as, ‘DB start date/time’) is the DB start date and the time of the first dose of intranasal study medication.

Double-blind Follow-up Phase

The start date of the double-blind follow-up phase (referred to as ‘DB FU start date’) is the day after the DB end date. The double-blind follow-up phase end date (referred to as ‘DB FU end date’) is the maximum of the last DB follow-up visit date or the end of trial date.

Posttreatment Phase

The start date of the posttreatment phase (referred to as ‘PT start date’) is the day after the DB end date. The posttreatment phase end date (referred to as ‘PT end date’) is defined as: for subjects who entered OL phase, the day of OL start date (defined below); for subjects who did not enter OL, including responders who withdraw within 4 weeks after the last dose of DB intranasal drug, the maximum of the last posttreatment visit date or the end of trial date.

For subjects who entered OL phase, PT end date/time is one minute before OL start date/time (defined below).

Open-Label Induction Phase

The start date of the open-label induction phase (referred to as ‘OL start date’) is the date of the first dose of intranasal study medication in a second induction treatment course. The open-label induction phase end date (referred to as ‘OL end date’) is the maximum of the date of the last visit in the open-label induction phase and the date of completion/withdrawal from the open-label induction phase.

The start date/time of the open-label induction phase (referred to as, ‘OL start date/time’) is the OL start date and the time of the first dose of intranasal study medication in the second induction treatment course.

Open-Label Follow-up Phase

The start date of the open-label follow-up phase (referred to as ‘OL FU start date’) is the day after the OL end date. The open-label follow-up phase end date (referred to as ‘OL FU end date’) is the maximum of the last OL follow-up visit date or the end of trial date.

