1.2. Trial Design

This is a randomized, double-blind, placebo-controlled, multicenter study designed to evaluate the efficacy, safety and tolerability of fixed dose of intranasal esketamine (28 mg, 56 mg, or 84 mg) as an add-on therapy to an oral antidepressant in Japanese subjects with TRD. A total of 183 subjects are planned to be enrolled in this study.

The study consists of the following phases: a screening phase (up to 4 weeks); a 6-week prospective oral antidepressant lead-in phase; a 4-week double-blind induction phase; a posttreatment phase (up to 24 weeks comprising of only oral antidepressant therapy), including an optional 4-week open-label induction phase; and a 4-week follow-up phase.

Thus, the duration of a subject's participation will be a maximum of 42 weeks, depending on whether they meet phase-specific criteria for response or relapse. The end-of-study (EOS) will occur when the last subject in the study completes his/her last study assessment (ie, last follow-up Visit).

Screening Phase

Japanese men and women aged 20 to 64 years old (both inclusive), who meet Diagnostic and Statistical Manual of Mental Disorders (fifth edition) (DSM-5) diagnostic criteria for recurrent major depressive disorder (MDD) without psychotic features, based upon clinical assessment, and confirmed by the MINI will be screened according to the inclusion/exclusion criteria.

To confirm eligibility for participation in the prospective lead-in phase, subjects will have a review of the inclusion/exclusion criteria in the screening phase. Subjects must not have responded to ≥ 1 but < 5 different oral antidepressants taken at adequate dosage and for adequate

duration, as assessed on the Massachusetts General Hospital – Antidepressant Treatment Response Questionnaire (MGH-ATRQ) and documented by medical history/prescription records, for the current episode of depression. The subject's current major depressive episode, depression symptom severity (MADRS total score ≥ 28 required), and treatment response to antidepressant medication used in the current episode (retrospectively assessed) must be deemed valid for participation in the clinical study based on the SAFER interview, which is administered by a remote, independent rater. At the screening visit, subjects who continue to fulfill all inclusion criteria and none of the exclusion criteria will be enrolled.

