Following subjects will have follow-up Visits; subjects who withdraw from double blind induction phase, nonresponders after double-blind induction phase, responders who withdraw within 4 weeks after the last dose of double blind intranasal drug and all subjects who receive open label intranasal drug. During this phase, further clinical/standard-of-care treatment will be provided by the study investigator however, in order to better assess potential withdrawal symptoms from intranasal study drug, the oral antidepressant medication must be continued for the follow-up phase unless determined as not clinically appropriate.

A schematic overview of the study design is provided in [Figure 1](#).

Figure 1: Schematic Overview of the Study Design

Esk: esketamine; IN: intranasal; AD: Antidepressant Day 1: The first day in the double-blind induction phase.

* Only responders after completion of the double-blind induction phase are eligible to join the posttreatment phase.

In the posttreatment phase, subjects who relapse within 20 weeks after the start of the posttreatment phase will receive an open-label treatment course of esketamine. Subjects who relapse more than 20 weeks after the start of the posttreatment phase will withdraw from the study and clinical/standard-of-care treatment will be arranged by the study investigator after relapse. The beginning of the open-label induction phase should be at least 2 weeks after the last dose in the double-blind induction phase.

** Following subjects will have follow-up Visits; subjects who withdraw from double blind induction phase, nonresponders after double-blind induction phase, responders who withdraw within 4 weeks after the last dose of double blind intranasal drug and all subjects who receive open label intranasal drug.

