| | | OL F/U 14 | Week 2 (OL F/U) | 11-21 | 14 |
| | | OL F/U 28 | Week 4 (OL F/U) | 22 to end of OL F/U | 28 |
| OL F/U final visit | | End Point (OL F/U) | 1 to end of OL F/U | | |
| MOAA/S ^c Oxygen Saturation ^d (predose and every 15 minutes to 1.5H) BPRS+ and CADSS (predose, 40M, 1.5H) CGADR ^e (1H, 1.5H) | DB | 1 | Baseline (DB) | ≤1 | 1 |
| | | 4 | Day 4 (DB) | 2-6 | 4 |
| | | 8 | Day 8 (DB) | 7-9 | 8 |
| | | 11 | Day 11 (DB) | 10-13 | 11 |
| | | 15 | Day 15 (DB) | 14-16 | 15 |
| | | 18 | Day 18 (DB) | 17-20 | 18 |
| | | 22 | Day 22 (DB) | 21-23 | 22 |
| | | 25 | Day 25 (DB) | 24 to end of DB | 25 |
| | | DB final visit | End Point (DB) | 2 to end of DB | |
| | OL | OL 1 | Baseline (OL) | ≤1 (predose) | 1 |
| | | OL 4 | Day 4 (OL) | 2-6 | 4 |
| | | OL 8 | Day 8 (OL) | 7-9 | 8 |
| | | OL 11 | Day 11 (OL) | 10-13 | 11 |
| | | OL 15 | Day 15 (OL) | 14-16 | 15 |
| | | OL 18 | Day 18 (OL) | 17-20 | 18 |
| | | OL 22 | Day 22 (OL) | 21-23 | 22 |
| | | OL 25 | Day 25 (OL) | 24 to end of OL | 25 |
| | | OL final visit | End Point (OL) | 2 to end of OL | |
| PWC-20 | DB | 25 | Day 25 (DB) | 2 to end of DB | 25 |
| | | DB F/U | DB F/U 7 | Week 1 (DB F/U) | DB F/U start day-10 |
| | DB F/U | DB F/U 14 | Week 2 (DB F/U) | 11-21 | 14 |
| | | DB F/U 28 | Week 4 (DB F/U) | 22 to end of DB F/U | 28 |
| | | DB F/U final visit | End Point (DB F/U) | 1 to end of DB F/U | |
| | PT | 32 | Week 1 (PT) | PT start day to 35 | 32 |
| | | 39 | Week 2 (PT) | 36-42 | 39 |
| | | 46 | Week 3 (PT) | 43-49 | 46 |
| | | 53 | Week 4 (PT) | 50-60 | 53 |
| | | 67 | Week 6 (PT) | 61-74 | 67 |
| | | 81 | Week 8 (PT) | 75-95 | 81 |
| | OL | OL 25 | Day 25 (OL) | 2 to end of OL | 25 |
| | OL FU | OL F/U 7 | Week 1 (OL F/U) | OL FU start day-10 | 7 |
| | | OL F/U 14 | Week 2 (OL F/U) | 11-21 | 14 |
| | | OL F/U 28 | Week 4 (OL F/U) | 22 to end of OL F/U | 28 |
| OL F/U final visit | | End Point (OL F/U) | 1 to end of OL F/U | | |
| Pharmacokinetics | DB | 4 | Day 4 (DB) | 2-6 | 4 |
| | | 25 | Day 25 (DB) | 24 to end of DB | 25 |
| | OL | OL 25 | Day 25 (OL) | 24 to end of OL | 25 |

^a For DB and posttreatment phases, the time interval is relative to the first day of DB phase. For other phases, the time interval is relative to the first day of that phase.

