2.4.4. Follow-up Analysis Set

The following FU analysis sets are defined for each phase and will be used for both safety and efficacy analyses.

- FU (DB): All subjects who do not respond at the end of DB induction phase and enter the DB follow-up phase
- FU (OL): All Safety (OL) subjects who enter the OL follow-up phase

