4.3.3. Time to Relapse

4.3.3.1. Definition

Time to relapse will be defined as the time between the end of the double-blind induction phase and the first documentation of a relapse event during the posttreatment phase. The relapse is defined as any of the following:

- MADRS total score ≥ 22 for 2 consecutive assessments. The date of the second MADRS assessment will be used for the date of relapse.
- Hospitalization for worsening depression or any other clinically relevant event determined per clinical judgment to be suggestive of a relapse of depressive illness such as suicide attempt, completed suicide, or hospitalization for suicide prevention. If hospitalized for any of these events, the start date of hospitalization will be used for the date of relapse. Otherwise the date of the event will be used if the subject is not hospitalized.
- In case both relapse criteria are met, the earlier date will be defined as the date of relapse for this subject.

Those subjects without relapse will be censored at the last visit (complete/withdraw) date in posttreatment phase.

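### SAP 2.1.2 counts the follow-up visits of early-withdrawing responders as posttreatment data, and SAP 4.3.3.1 leaves unclear whether relapse events and censoring stop on the same date

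*SAP*

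**What the plan says.** **Phase dates.** SAP 2.1.2 defines the PT end date for everyone who does not enter the open-label (OL) phase as follows: "including responders who withdraw within 4 weeks after the last dose of DB intranasal drug, the maximum of the last posttreatment visit date", with the subject's end of trial as the other term of that maximum. SAP 2.1.1 adds: "The reference end date for the study is the end of trial date including the last follow-up visit".

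**No other place for these visits.** SAP 2.1 reserves the double-blind (DB) follow-up phase for "Non-Responders or subjects who withdraw from DB induction phase". SAP 2.4.4 defines FU (DB) as "All subjects who do not respond at the end of DB induction phase and enter the DB follow-up phase". A responder who withdraws from PT fits neither.

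**The protocol's view.** Protocol 6.5 and 9.1.8 place responders who withdraw within 4 weeks of the last DB dose in the follow-up phase. Schedule 2 gives that phase visits at F7, F14 and F28. SAP 1.2 repeats this and says of the phase that "further clinical/standard-of-care treatment will be provided by the study investigator", with the oral antidepressant to continue unless that is clinically inappropriate. By contrast, SAP 1.2 describes PT as "a posttreatment phase (up to 24 weeks comprising of only oral antidepressant therapy". Under Protocol Attachment 1, prohibited medications are, unless specifically noted, barred only up to the start of follow-up.

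**Time to relapse.** SAP 4.3.3.1 counts the first relapse documented in the PT phase. For the rest: "Those subjects without relapse will be censored at the last visit (complete/withdraw) date in posttreatment phase". SAP 4.3.3.2 summarises the result by Kaplan-Meier, by treatment arm and for the esketamine arms combined, separately for remitters and for responders not in remission.

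**The concern.** Durability of effect after intranasal treatment stops is a stated secondary objective, and the setting is stable oral antidepressant alone. Under SAP 2.1.2, the PT summaries of MADRS, CGI-S, PWC-20, POMS-2 and adverse events take in observations made after a responder has left that setting.

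This includes responders who relapse before 2 weeks after the last dose. Protocol 6.4.1 moves them to follow-up, so their post-relapse MADRS scores enter PT windows. Yet footnote f to SAP Table 1 says PT MADRS assessments run only to Week 24 or relapse.

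For time to relapse, two definitions interact. The event window is the PT phase as extended by 2.1.2. The censoring date is worded separately and can be read two ways. A Kaplan-Meier estimate needs one observation limit that applies whether or not the subject relapses.

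**Working it through.** The plan states no figure on this point, so there is none to reproduce. The check is date arithmetic plus a comparison of the two censoring readings.

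**Inputs.** Last DB dose Day 25 (±1) and DB end Day 28 (Schedule 1). Follow-up at +7, +14 and +28 days, each ±3 (Schedule 2). MADRS PT windows: Week 1 up to Day 35, then Week x from 22 + 7x to 28 + 7x (SAP Table 1). Assumption: follow-up days are counted from PT withdrawal.

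**Limit for follow-up.** 25 + 28 = Day 53 (Days 52 to 54 with the dosing window).

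| PT withdrawal | F7, F14, F28 (study day) | MADRS PT week assigned | Days from DB end at withdrawal | Days from DB end at F28 |
|---|---|---|---|---|
| Day 32 | 39, 46, 60 | 2, 3, 5 | 4 | 32 |
| Day 39 | 46, 53, 67 | 3, 4, 6 | 11 | 39 |
| Day 46 | 53, 60, 74 | 4, 5, 7 | 18 | 46 |
| Day 53 | 60, 67, 81 | 5, 6, 8 | 25 | 53 |

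Each such subject's PT phase is lengthened by 28 days (±3), and 28/168 = 16.7% of the phase.

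**Corroboration.** Schedule 2 has PWC-20 in PT only at Visits 4.1 to 4.4, the last on Day 53. SAP Table 1 nevertheless has PT windows for it at Week 6 ("67 | Week 6 (PT) | 61-74 | 67") and at Week 8, target Day 81. Days 67 and 81 are exactly F14 and F28 after a Day 53 withdrawal. Apart from unscheduled visits, only follow-up visits can fill those windows.

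**Two readings of the censoring rule.**

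- *Reading A, the PT withdrawal visit.* A withdrawn subject without relapse leaves the risk set at withdrawal. A relapse in the following 4 weeks still lies in the PT phase as 2.1.2 defines it. For example, a MADRS of 22 or more at the last PT assessment, confirmed at F7, would count.
- *Reading B, the last visit in the extended phase.* A withdrawn subject without relapse stays at risk about 28 more days, with checks at F7, F14 and F28 instead of weekly. Because the MADRS criterion needs two consecutive scores, a rise first seen at F14 is confirmed only at F28.

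**Illustration (hypothetical).** Take six subjects in one arm and remission stratum. Two relapse at Weeks 3 and 5, one withdraws at Week 2, and three are followed to Week 24. Relapse-free proportion at Week 6:

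| Rule | Withdrawn subject does not relapse | Withdrawn subject relapses at Week 4 |
|---|---|---|
| Events and censoring both stop at withdrawal | 4/5 × 3/4 = 0.60 | 4/5 × 3/4 = 0.60 |
| Reading A | 4/5 × 3/4 = 0.60 | 5/6 × 4/5 × 3/4 = 0.50 |
| Reading B | 5/6 × 4/5 = 0.667 | 5/6 × 4/5 × 3/4 = 0.50 |

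One subject can move the estimate either way. The Greenwood standard error of the 0.60 is 0.60 × √(1/(5×4) + 1/(4×3)) = 0.22, so the shift is small beside the sampling error.

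**The case against.** The strongest reply is that 4.3.3.1 already censors at withdrawal. Its parenthesis most naturally means the PT completion or withdrawal visit, and Schedule 2 has a PT early-withdrawal visit. A reader might infer from 2.1.2 that follow-up certainly counts as relapse-free time at risk and that durability is therefore overstated. The documents do not support that. The censoring rule names neither the PT end date nor the end of trial. Even on reading B, the upward shift appears only if no relapse is scored during follow-up, and MADRS is scheduled at all three visits. What stands after this reply is the mismatch: the natural reading of the censoring rule leaves the event window longer than the censoring window.

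A reader might also infer that these visits reflect changed treatment. The documents permit a change but do not establish one, since continuing the same oral antidepressant is the default. What has changed is the set of restrictions.

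Responders who left because they relapsed within 2 weeks already have an event, so they gain no time at risk on either reading. For them only the visit summaries are affected.

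The express wording in 2.1.2 and the phase split in SAP Amendment 1 suggest a deliberate choice. Keeping responders on a days-from-DB-start axis is defensible for withdrawal symptoms on the PWC-20. That does not justify the same treatment for efficacy scores and relapse.

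**Conclusion.** The classification defect is established from the text. Follow-up visits of responders who withdraw within 4 weeks are analysed as PT data, contrary to the protocol's phase structure, and neither 2.1 nor 2.4.4 gives them another home. The relapse defect is one of definition: either events and non-events have different limits, or withdrawn subjects stay at risk about 28 more days under sparser assessment. The SAP does not say which.

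The consequences are limited. The primary analysis is untouched and time to relapse is descriptive, with no test. The documents do not give the number of such responders, and neither the direction nor the size of any bias is established. The strata are split by arm and remission status and may be small, which is why single subjects can be visible. The 28-day figure assumes follow-up is counted from PT withdrawal and completed to F28. The point merits correction because the change is cheap and durability is a stated objective.

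**What to change.** 1. **SAP 2.1.2:** for subjects who neither enter OL nor complete PT, end the PT phase at the date of PT withdrawal.
2. **SAP 4.3.3.1:** state that relapse events and censoring both stop at that date for these subjects.
3. **SAP 2.1 and 2.4.4:** add a separately labelled responder follow-up group for Visits 6.1 to 6.3. Do not pool it with nonresponders in FU (DB). DB follow-up is counted from the day after DB end, so pooling would place responders already up to about 4 weeks off intranasal drug at Week 1 beside nonresponders who had just stopped.
4. **PWC-20:** if pooling on the days-from-DB-start axis is intended, say so and limit it to that scale.

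The cost is SAP wording, changed phase flags and one additional small follow-up display. No new data are needed.

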2.1.3. Study Day and Relative Day

Study day is calculated relative to the reference start date for the study. Relative day is calculated relative to the start date of the analysis phase in which the data are captured. A minus (-) sign indicates days prior to the start of study or prior to the start of the analysis phase.

Study day for an event on or after the start of the study is calculated as:

$$\text{event date} - \text{reference start date} + 1.$$

Study day for an event prior to the start of the study is calculated as:

$$\text{event date} - \text{reference start date}$$

Relative day for an event on or after the analysis phase start date is calculated as:

$$\text{event date} - \text{analysis phase start date} + 1.$$

Relative day for an event prior to the analysis phase start date is calculated as:

$$\text{event date} - \text{analysis phase start date}.$$

There is no study Day 0 or relative Day 0.

